5. COLLECTION AND RECORDING OF STUDY VARIABLES

The patients must sign informed consent before any study specific investigations are performed. The investigator will ensure that all data collected in the study, are recorded in a timely manner according to any instructions provided. Electronic Case Report Forms (eCRF) will be used in this study (See Section 7.2).

5.1 Study measurements

5.1.1 Clinical data

At the enrolment visit the patients will undergo a clinical examination which consists of; recording of demographic data (date of birth, sex and ethnicity), medical history and concomitant diseases, smoking status, heredity of AAA, current medication, recording of weight & height, heart rate & blood pressure, cardio-pulmonary status and general appearance.

At all points of contact with phone or visit at the clinic any AE and SAE are recorded, target dose of study drug is determined and compliance is asked for. Discontinuation (temporarily or permanent) of study medication ≥ 3 consecutive days will be recorded.

At visits medical events and any changes in smoking status will be noted and vital signs and weight is recorded. Compliance to study drug is noted and remaining tablets are counted. At completion visit and at 24 months, the above plus a physical examination is performed. Changes in current medication are recorded yearly.

At enrolment visit, at 24 months and completion quality of life will be recorded with EQ-5D and RAND -36, see appendix 1.

At enrolment blood samples will be taken for fP-Glc and P-Creatinine, analysed at accredited hospital laboratory. P-Creatinine will be tested for safety every 12 months. A 24 months S-B12 is controlled for possible metformin induced deficiency. In Uppsala and Malmö venous blood samples will be taken at baseline, 24 months and completion for scientific reasons.

5.1.2 Imaging

At baseline, 24 months and completion, the aorta will be examined by non-contrast enhanced CT with 1 mm slices or thinner from the jugulum to the groins.

At enrolment, 24 months and completion the abdominal aorta will be examined by US. The assessment of abdominal aortic diameter with US will be done by the local US technician, using the standardized technique measuring the largest anterior-posterior diameter from leading edge to leading edge perpendicular to the blood flow in the aneurysm. Inclusion criteria will be based on US determined diameter.

If a subject withdraws from the study due to operative need of the aorta, the preoperative CT will be used for analysis in the study. The assessment of aortic diameter on CT will be done using outer edge to outer edge perpendicular to blood flow. Volumetric AAA analysis of CT images will be performed using manual drawing of the vessel wall contours in axial slices of the entire abdominal aortic as well as semiautomatic measures in 3mensio, Pie Medical, Maastricht. Analysis will start at the slice just below the most distal renal artery excluding accessory renal arteries and end at the slice just above the aortic bifurcation. Measures of perivascular adipose tissue will be made adjacent to the aorta.

All CT assessment (diameter and volume) will be done at a core lab at the Department of Radiology, Uppsala university hospital, Uppsala. The CT identification is the four digits enrolment code. The reviewer will be blinded regarding treatment allocation.

CT images will also be reviewed by local radiologists according to GCP at respective hospital. Accidental findings of unrelated pathology on the CT scan will be dealt with as appropriate by investigator at respective site.

5.1.3 Telephone contacts

The patients allocated to metformin will initially be contacted by the study nurse every two weeks in the run in phase. Thereafter phone contacts are every six months the first two years and yearly thereafter. The purpose for these calls is to support the patients in the run in phase for those allocated to metformin treatment, record drug accountability and if any AE or SAE had occurred since last visit and if previous AE or SAE are resolved.

5.2 Safety

A Summary of product characteristics (SmPC) including safety data of the study drug is stored at respective site in the investigators brochure.

5.2.1 Definition of adverse events

An AE is any unwanted medical occurrence that does not necessarily have to have a causal relationship with the investigational product. An AE can be any unfavourable, unintended clinical sign, symptom, medical complaint or clinically relevant change in laboratory variables or clinical tests. Accidents, operations not pre-planned or deterioration in concurrent illness are also considered as AEs. Known gastrointestinal side-effects of metformin are actively asked for and noted separately.

5.2.1 Assessment of intensity

The Investigator should rate the intensity of any AE as follows:

Mild: The AE does not interfere with the patient's usual function.

Moderate: The AE interferes to some extent with the patient's usual function.

Severe: The AE interferes significantly with the patient's usual function.

When an AE occurs, the information must be recorded at the AE page. Every AE must be followed up and at study end if the AE still occurs, note in the e-CRF, AE outcome – not resolved.

5.2.2 Assessment of causality

The investigator shall judge whether, in his/her opinion; the AE is potentially associated with the study drug. When stating the causality, the following nomenclature should be used:

Unrelated: There is little or no chance that the study treatment

caused the AE.

Possibly related: The association of the AE with the study treatment is unknown,

however, the AE is not clearly due to another condition.

Probably related: A reasonable temporal association exists between the AE and the

study treatment. Based on the Investigator's clinical experience, the

association of the AE with the study treatment seems likely.

5.2.3 Definitions of serious adverse event

A serious adverse event is an AE occurring during any study phase (i.e., run-in, treatment, washout or follow-up), that fulfils one or more of the following criteria:

- Results in death
- Is immediately life-threatening
- Requires in-patient hospitalization or prolongation of existing hospitalization
- Results in persistent or significant disability/incapacity or substantial disruption of the ability to conduct normal life functions
- Is a congenital abnormality or birth defect
- Is an important medical event that may jeopardize the patient or may require medical intervention to prevent one of the outcomes listed above

The causality of SAEs (their relationship to all study treatment/procedures) will be assessed by the investigator(s).

5.2.4 Recording of adverse events

AE + SAE will continuously be recorded from enrolment at all points of contact thru to completion at 24 months and documented in the eCRF and AE and SAE log.

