1.2.1 Primary objective

To examine if up to 2g metformin administered daily over a five-year period slows AAA growth measured as computed tomography (CT) imaging assessed AAA diameter in patients with small AAAs who do not have diabetes.

An interim STOP/GO analysis will be performed after two-years of treatment.

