1.2.4 Safety objective

To determine adverse events; primarily related to known side effects of metformin and possible unexpected effects on AAA, related to metformin treatment after two and five years.

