2. STUDY PLAN AND PROCEDURES

2.1 Study design

The MAAAGI-trial is a population-based multi-center, prospective, parallel group, randomized, open label trial with blinded outcome assessment to assess if metformin up to 2g daily over a five-year period will reduce AAA growth in patients who do not have diabetes.

Patients will be recruited from a cohort of patients with diagnosed AAA at the following seven Swedish sites; 1) Uppsala University hospital, Uppsala, 2), Skåne University hospital, Malmö, 3) Gävle county hospital, Gävle, 4) Västerås county hospital, Västerås. 5) Karlstad county hospital, Karlstad 6) Falun county hospital, Falun, and 7) Umeå University Hospital, Umeå.

The patients should have a maximum aortic diameter of 30-49mm for men and 30-44mm for women, not have diabetes and be expected to tolerate metformin.

A total of 500 patients with AAA will be included in the study, 250 in each study arm. Patients will be randomised to metformin or standard care in a 1:1 ratio.

The patients are scheduled for one enrolment visit, eight study visits and ten phone contacts for those randomized to metformin (three to support titration of study drug) and seven phone contacts for those randomized to standard care. The study visits will take place at the vascular laboratory at the respective surgical departments for clinical examination and blood sampling and at the CT units at the radiology departments where CT-imaging will be performed.

After a run in phase to support titration of metformin, visits and phone contacts are scheduled to alternate every three months until 24 months and twice yearly thereafter. CT imaging and AAA US will be performed at baseline, 24 months and end of study, as well as if necessary according to clinical routine. Study drug will start at baseline and continue through completion.

End of study is defined as 1) study completion at 60 months, or 2) discontinuation from study before that for any reason, for example due to AAA repair or patients will.

When all patients have completed the 24-month follow-up (including imaging) an interim analysis will be performed to assess for efficacy and safety; if there is no trend towards a positive effect or signs of a harmful effect of metformin, the study will be stopped at this phase.

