The study will be performed in accordance with the ethically acceptable principles that have their origin in the Declaration of Helsinki and according to national legislations and international regulations. In addition, the study will be performed in accordance with this study protocol.

	Enrolment	Baseline/ Visit 1	Phone 2*	Phone 3*	Phone 4*	Phone 5	Visit 6	Phone 7	Visit 8	Phone 9	Visit 10	Phone 11	Visit 12	Phone 13	Visit 14	Phone 15	Visit 16	Phone 17	Completion
Visit window		$Day 0^{l}$	2 weeks	4 weeks	6 weeks	3 months	6 months	9 months	12 months	15 months	18 months	21 months	24 months	30 months	36 months	42 months	48 months	54 months	60 months
Informed consent	X																		
In- & exclusion criteria	x																		
Demographics ²	x																		
Smoking status	x						X		X		X		x		X		Х		X
Medical history	x																		
Current medication	x								X				x		X		Х		X
Physical examination ³	x												x						X
Vital signs ⁴	x						X		X		X		x		X		x		X
QoL questionnaires ⁵	x												x						X
CT scan		x											x						X
Blood samples ⁶	x								X				x		X		X		X
Randomisation		x																	
Ultrasound ⁷	x												x						X
Drug prescription*		x					X		X		X		x		X		Х		
Drug accountability*			X	X	X	X	X	X	X	X	X	X	X	X	X	X	х	X	X
Target dose of study drug*		X	X	X	X	X	X	X	X	X	X	X	X	X	X	X	х	X	
AE registration	X	X	X	X	X	X	X	X	X	X	X	X	X	X	X	X	х	X	х
SAE registration	x	x	x	x	x	X	X	X	x	X	X	x	x	x	x	X	x	x	X

Table 1. Overview of study activities. Phone 2-5 are to be performed +/- 5 days from target date and the remaining activities +/- 4 weeks from target date.

¹ Within four weeks of enrollment

² Demographics includes date of birth, sex and ethnicity

³ Physical examination includes cardio-pulmonary status and general appearance

⁴ Vital signs include blood pressure, heart rate, height (only at enrollment) and body weight

⁵ EQ-5D and RAND-36

⁶ Safety lab at all sites and blood samples for biobank at Uppsala and Malmö

⁷ Final Ultrasound +/- one week from CT scan

^{*} For those randomized to metformin only, see item 4.1.1 below

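### Section 5.2.4 ends AE and SAE recording at 24 months, in conflict with the 60-month study period in section 2.1, Table 1, sections 5.1.1 and 5.1.3 and the five-year safety objective

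*Combined protocol and SAP*

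**What the plan says.** Section 5.2.4, whose title is the recording of adverse events, states: "AE + SAE will continuously be recorded from enrolment at all points of contact thru to completion at 24 months".

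Other parts of the same document give a longer period:

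- Section 2.1 defines the end of study as "study completion at 60 months", or earlier discontinuation from the study. On dosing it says: "Study drug will start at baseline and continue through completion".
- Section 1.2.1 describes "metformin administered daily over a five-year period".
- Table 1 has rows for "AE registration" and "SAE registration". Both are marked in every column from enrolment to completion at month 60. Neither carries the asterisk that limits a row to the metformin arm.
- Section 5.1.1 has AEs and SAEs recorded at every telephone or clinic contact. Section 5.1.3 has them asked about at the calls, which go on after the second year. Neither sets a 24-month limit.
- Section 1.2.4 asks for adverse events "related to metformin treatment after two and five years".

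**The concern.** In this protocol 24 months is the interim time point, not completion. By the protocol's own definition, a completion at 24 months does not exist for a patient who carries on. Someone at a site who wants to know when logging ends will naturally turn to the section with that title, and there the answer is 24 months, while metformin continues for three more years.

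What is at stake is uniform safety data in years 3 to 5. Drug-related AEs are a named safety variable (section 8.2.3). An unexpectedly high proportion of them is a ground for stopping the trial (section 9). SUSAR assessment and the yearly safety report (section 5.2.6) depend on sites capturing events. The protocol itself expects at least one late effect, vitamin B12 deficiency after prolonged treatment (section 5.2.9). Events not logged when they happen are hard to recover reliably afterwards.

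**Working it through.** The 24-month figure in 5.2.4 is not derived from anything, so there is no calculation to reproduce. The check compares the sections and counts contacts.

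**Sections side by side**

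| Place | Recording or study period |
|---|---|
| 5.2.4 | enrolment to 24 months, called completion |
| 2.1 | completion is 60 months; drug given until completion |
| Table 1 | AE and SAE registration at every contact to month 60 |
| 5.1.1 | AE and SAE at all contacts, no time limit |
| 5.1.3 | AE and SAE at telephone contacts, which continue after year 2 |
| 5.2.3 | an SAE can occur in any study phase |
| 5.2.6 | all SAEs documented, no time limit |
| 1.2.4 | adverse events after two and five years |

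Only 5.2.4 gives 24 months as the end.

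**Time outside the 5.2.4 window**

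- Months: 60 − 24 = 36, and 36/60 = 60% of the planned treatment period.
- Contacts in the metformin arm: section 2.1 gives 8 visits and 10 calls, so 18. The Table 1 columns from baseline to completion also number 18.
- Contacts in the standard-care arm: 8 visits and 7 calls, so 15.
- Contacts after month 24: months 30, 36, 42, 48, 54 and 60, so 6 in each arm. That is 6/18 = 33% of metformin-arm contacts and 6/15 = 40% of standard-care contacts. Table 1 marks all six for both AE and SAE registration.

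**Range of the possible loss**

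- Every site follows Table 1: 0 months lost.
- Every site follows 5.2.4 literally, with no drop-out: 250 × 3 = 750 of 250 × 5 = 1,250 metformin person-years. For both arms together it is 500 × 3 = 1,500 of 2,500.
- Every site follows 5.2.4, with the 30% drop-out of section 8.4. As an assumption, drop-out is equal in the two arms and has all happened by month 24. Then 250 × 0.70 = 175 metformin patients remain, and 175 × 3 = 525 person-years are unrecorded.

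The ceiling for the metformin arm is thus 525 to 750 person-years, depending on when patients leave, and the floor is zero. The documents do not show how many sites would read the protocol either way, so no point within this range can be called likely.

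**The case against.** The strongest reply is that the protocol already requires recording to month 60 in several places. Table 1, 5.1.1 and 5.1.3 all do so, 5.2.3 and 5.2.6 are unlimited, and the instruction on AE intensity expects events still present at study end to be noted in the eCRF. Even 5.2.4 speaks of all contacts up to completion, so only its number is wrong. This stands. It rules out calling 5.2.4 the controlling rule, because no section is ranked above another. It also rules out treating 24 months as a deliberate safety window. The figure may be left over from another design or borrowed from the interim time point, but the documents do not say.

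A reader might infer two further consequences that the documents do not support:

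- **That the five-year safety objective could not be answered.** This would need every site to follow 5.2.4 against Table 1 and 5.1.1. Even then, GFR is a safety variable and creatinine is tested every 12 months.
- **That the AE comparison between arms would be biased downwards.** A site that stopped on the wording of 5.2.4 would presumably stop in both arms. Equal under-recording lowers counts and precision and can shrink a risk difference, but it need not change a ratio. The direction depends on the effect measure and on event timing, and neither is specified.

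The reply does not remove the contradiction. Where two instructions conflict and neither is ranked, practice can differ among seven sites, and a majority of sections on one side does not prevent that.

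**Conclusion.** The point holds as an internal contradiction in a safety rule. Section 5.2.4 is wrong as written, because it attaches 24 months to a completion that section 2.1 sets at 60. Depending on which section a site follows, between 0 and 36 of 60 months of AE and SAE recording, and between none and all six of the later contacts, could be lost for a patient who stays to month 60. The upper figure assumes a literal reading of 5.2.4 and the lower one assumes that Table 1 is followed. The established consequence is a risk of uneven safety ascertainment across sites in years 3 to 5. A certain loss of three years of data is not established. The contradiction should be corrected because it concerns when serious events stop being recorded while patients are still being treated, and because correcting it costs little.

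**What to change.** Reconcile 5.2.4 with section 2.1 and Table 1. It should say that AEs and SAEs are recorded from enrolment to end of study as defined in section 2.1 (60 months, or earlier discontinuation from the study), in both arms and whether or not study drug has been stopped. Tell all seven sites.

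The end of recording should not be tied to the end of dosing. The standard-care arm takes no study drug (section 4.1), so such a rule would be undefined for half the trial. Patients who stop metformin are asked to stay and follow the remaining procedures (section 4.2). Ending their logging would drop events among patients who may have stopped because of side effects, and would make ascertainment differ by arm.

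The cost is a one-line amendment, with the approval that section 6.1 requires, and a site notice. No visit or call is added, since Table 1 already schedules registration at all six later contacts. The eCRF is not among the documents, so the sponsor should check that its AE and SAE forms stay open after month 24. If any patient has already passed month 24, the sponsor should also check that logging continued.

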5.2.5 Follow-up of unresolved adverse events

For all AEs, the patient will be followed until either the AE has ceased or until the patient is under professional medical care and a potential causality between the study treatment and the AE has been assessed.

5.2.6 Reporting of serious adverse events

All SAEs will be documented. The investigator is responsible for informing the Regional Ethical Review Board, and/or the Regulatory Authority of the SAE as per local requirements.

The Sponsor is responsible for SAEs reporting to the authorities and SUSARS (Suspected Unexpected Serious Adverse Events) reporting. A SUSAR will be reported to authorities if the SAE is assessed by the Sponsor to be a SUSAR, i.e. the event is related to the study drug and not described in the product specification. The CIOMS form will be used with assistance from the Swedish medical products agency.

A yearly safety report is submitted to the regional ethical review board and medical products agency.

5.2.7 Temporary withdrawal

The patient will be informed to temporarily withdraw the study drug 48h following intra venous contrast media injection, in case of vomiting, diarrhoea, fever, reduced fluid intake or suspect or manifest dehydration or lactic acidosis according to clinical routine for metformin treatment. The study drug is continued following resolution of the risk for dehydration and/or temporary renal impairment. See table 2

5.2.9 Laboratory safety assessment

At enrolment and every 12 months P-Creatinine will be analysed. Metformin may induce vitamin B12 deficiency after prolonged treatment and S-B12 is therefore assessed at 24 months. The blood volume will not exceed 40 mL at each visit, including concurrent blood samples for scientific reasons. Extra blood panels will be drawn at the discretion of the

investigator if there is concern for primarily renal or hepatic impairment due to alterations in clinical status or medication. Elevated fP-Glucose or P-Creatinine discovered at inclusion visit or throughout the study will be dealt with according to clinical praxis. Typically by referral to the patients family doctor.

The analyses will be performed at the local hospital laboratories and follow the Swedish biobank law for collecting blood samples in a clinical study. Tubes will be labelled and handled according to local routines and will be discarded after analysis.

Blood samples will be taken for scientific reasons in Uppsala and Malmö. Samples are centrifuged, frozen and stored for subsequent analysis in accordance with the Swedish biobank law for collecting blood samples in a clinical study.

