4.1.4 Concomitant treatment(s)

Medication, which is considered necessary for the patient's safety and well-being, may be given at the discretion of the investigator(s).

All medication is allowed, except for antidiabetic agents. If the need for antidiabetic medication should arise, the patient is discontinued from the study.

The study protocol includes patient history and measures of cardiovascular function such as blood pressure, heart rate and cardiac and respiratory auscultation. If un- or undertreated diseases or risk factors are discovered, treatment will be initiated as appropriate or the patient is referred to relevant care. Active smokers are encouraged to smoking cessation.

It is likely that CT imaging will generate accidental findings in some patients. These findings will be dealt with according to clinical praxis at respective site. It is the responsibility of the investigator at respective site to make sure relevant care is provided for patients with accidental findings on imaging, laboratory tests or physical examination.

Concomitant medications will be recorded in the medication list in the eCRF.

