6.3 Risks – Benefits

The uncertain knowledge state supporting the study-hypothesis emphasizes the importance of a risk assessment for each patient. A risk determination of potential risks in this study has been made. These risks together with the actions to minimize these risks are compiled below:

RISKS	ACTION
Suspected drug related adverse event, such as gastrointestinal events	If not tolerated, treatment with study drug should be reduced in dose or stopped, temporarily or permanent, and appropriate medical action should be initiated according to the nature and severity of the AE.
Patient require surgery or intravenous contrast media during study	Temporary discontinuation of the study drug according to clinical praxis for metformin. Typically 48 h after intravenous contrast media, in the perioperative phase and during fasting.
Patient develops suspect or manifest dehydration during study	If risk of dehydration for any reason the study drug is temporarily discontinued. This typically includes but is not limited to fever, serious infection, vomiting, diarrhoea and reduced fluid intake.
Patient develops suspect or manifest hypoxia during study	If risk of hypoxia for any reason the study drug is temporarily discontinued. This typically includes but is not limited to, sepsis, chock, myocardial infarction and decompensated heart failure.

Patient requiring continuous treatment with drugs that may temporarily affect renal function, such as NSAIDs	Study drug should be discontinued during treatment if there is evidence of renal impairment
Patient develops B12 deficiency secondary to metformin treatment BENEFITS	S-B12 levels are controlled every 24 months and replacement therapy is initiated if indicated

Other than obtaining an extensive medical evaluation and close monitoring of the AAA, no clear benefit was identified for the patients who participate in the study.

Table 2, possible risks and planned action

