8.2.3 Safety variables

Safety variables include differences in drug related AE and GFR.

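### The sections disagree on when S-B12 is tested, no test reaches month 60, and AE recording and comparison rules also fall short of the five-year safety objective

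*Combined protocol and SAP*

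**What the plan says.** **B12 schedule.** Two sections name one time point. Section 5.1.1: "A 24 months S-B12 is controlled for possible metformin induced deficiency". Section 5.2.9: "Metformin may induce vitamin B12 deficiency after prolonged treatment and S-B12 is therefore assessed at 24 months". The risk table in 6.3 gives a recurring rule: "S-B12 levels are controlled every 24 months and replacement therapy is initiated if indicated". Table 1 (section 2.1) marks blood samples at enrolment and at 12, 24, 36, 48 and 60 months. Its footnote says only "Safety lab at all sites and blood samples for biobank at Uppsala and Malmö" and lists no analytes.

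**Safety objective.** Section 1.2.4 is about AEs, and gives their scope as "primarily related to known side effects of metformin and possible unexpected effects on AAA, related to metformin treatment after two and five years".

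**Adverse events.** Section 5.2.4 runs AE and SAE recording from enrolment to completion, which it places at 24 months. Table 1 marks both at every contact to month 60, and 2.1 defines completion as 60 months. Section 8.2.3: "Safety variables include differences in drug related AE and GFR". Section 5.2.2 on causality: "The investigator shall judge whether, in his/her opinion; the AE is potentially associated with the study drug". Under 4.1 the control arm receives standard care, with no placebo.

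**The concern.** A site reading 5.1.1 and 5.2.9 would test B12 once. A site reading 6.3 would test again at month 48. Table 1 does not settle which is right. This matters because 6.3 offers B12 testing, with replacement if needed, as the action against a named risk, and 5.2.9 itself ties that risk to long exposure. Under the single-test rule, this protection ends three years before treatment does.

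The five-year safety objective then depends on adverse events, and that route has two faults. Read literally, 5.2.4 ends collection at month 24. In addition, the comparison in 8.2.3 is limited to events judged drug-related, in an open-label trial where one arm has no drug to which an event could be attributed.

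**Working it through.** There is no stated figure to reproduce. The check compares schedules and does simple arithmetic.

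**1. Test times within 60 months**

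| Source | S-B12 months | Last test to month 60 | Share of the 60 months |
|---|---|---|---|
| 5.1.1 and 5.2.9 | 24 | 60 − 24 = 36 months | 36/60 = 60% |
| 6.3 | 24, 48 | 60 − 48 = 12 months | 12/60 = 20% |

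Since 60 is not a multiple of 24 (60 − 2 × 24 = 12), the recurring rule also misses month 60. By contrast, 5.2.9 tests creatinine every 12 months, so that test does reach month 60.

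**2. Can the test be added without a new visit?** Yes. Table 1 already draws blood at 24, 48 and 60 months, and the blood row lacks the asterisk that marks metformin-only activities.

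**3. AE recording.** The 24-month end in 5.2.4 conflicts with Table 1, with the definition of completion in 2.1, and with 5.1.1, which records AEs at all contacts. Table 1 and the five-year objective agree with each other, so 5.2.4 is the text to correct.

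**4. The drug-related contrast.** Suppose the AE proportion is the same, r, in both arms. Let a share f of metformin-arm events and a share g of control events be rated drug-related. The 8.2.3 difference is then r·f − r·g = r(f − g), although the true difference is 0. Raters know the allocation and controls take no study drug, so g will probably lie well below f. The contrast would then show an excess on metformin that comes from the rating. Conversely, a metformin effect rated unrelated drops out of the comparison altogether. An all-cause comparison by randomised arm has neither fault.

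**5. Assays needed in the metformin arm.** Inputs: 250 per arm (2.1) and 30% dropout over five years (8.4). Linear dropout is an assumption.

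- Month 48: 30% × 48/60 = 24%, so 250 × 0.76 = 190.
- Month 60: 250 × 0.70 = 175.
- Total: 190 + 175 = 365. With no dropout, the upper bound is 250 + 250 = 500.
- If 6.3 is the intended rule, the month-48 tests are already planned and only the month-60 tests are new.

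**The case against.** **B12 is not an endpoint.** Section 1.2.4 concerns adverse events, and 8.2.3 names AEs and GFR. S-B12 is a monitoring test linked to replacement. This stands. A reader might infer that the plan promised a five-year B12 comparison and failed to deliver it, but the documents make no such promise. A between-arm B12 proportion would be a new variable and can only be optional.

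**Deficiency can still surface as an AE.** The AE definition in 5.2.1 covers clinically relevant laboratory changes, and Table 1 collects AEs in both arms to month 60. This stands for deficiency that someone detects. Without a scheduled test, silent deficiency is seen only by chance.

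**The control count is not forced to zero.** A reader might infer that no control event can be rated drug-related. The argument would be that controls get no study drug and that 4.1.4 says "All medication is allowed, except for antidiabetic agents". The documents do not go that far. Section 5.2.2 leaves the rating to the investigator's opinion and allows a possible relation where the link is unknown and no other condition clearly explains the event. Section 4.2 asks patients whose study treatment stops, including for new diabetes, to stay in follow-up, so later antidiabetic use is not clearly excluded. What stands is a likely bias towards zero.

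**The simplest repair is to adopt the 6.3 wording in 5.1.1 and 5.2.9.** That would remove the contradiction, but the final 12 months would still have no scheduled test.

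**Conclusion.** The inconsistency is real, and so is the absence of a month-60 test under either rule. Monitoring for a named risk ends 36 or 12 months before completion, depending on which section is followed. The 24-month end in 5.2.4 contradicts Table 1. The drug-related comparison in 8.2.3 is open to bias, with a direction that follows from the design and a size that the documents do not allow to be estimated.

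The gap should not be turned into patient-years and read as harm. The documents give no deficiency rate, and follow-up time is not the same as time on drug, because some patients will stop metformin.

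Severity is minor. The primary endpoint, sample size and power are unaffected. The schedule finding needs no assumption. The assay counts rest on 30% dropout accruing linearly.

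**What to change.** 1. Make 5.1.1, 5.2.9, 6.3 and a Table 1 footnote agree: S-B12 at 24, 48 and 60 months, at minimum in the metformin arm. State which arms are tested, and record any replacement therapy, because it can return a later value to normal.
2. Change 5.2.4 so that AE and SAE recording runs to 60 months.
3. In 8.2.3, compare AEs by randomised arm regardless of rated causality. Say explicitly that controls are included: 8.1 defines the Safety Analysis Set by receipt of study drug, which taken literally leaves them out. Causality ratings can still be tabulated descriptively.
4. If only the metformin arm is tested, list deficiency found solely by the scheduled test separately from the between-arm AE comparison. Otherwise such events are sought in one arm only.

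Optional: test controls as well, and report the between-arm proportion with low B12.

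**Cost.** No added visits, and short edits to 5.1.1, 5.2.4, 5.2.9, 6.3, 8.2.3 and one footnote. About 190 metformin-arm assays at month 48 (some already implied by 6.3) and about 175 at month 60. Low values will need follow-up. One limit remains: 2.1 gives the metformin arm ten phone contacts against seven for controls, so AE ascertainment during titration will not be fully equal even in an all-cause comparison.
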